# **APPENDIX II:**

# PART A (ADULTS) Clinical Toxicity Grading

Systemic Illness	Mild (Grade 1)	(Moderate (Grade 2)	Severe (Grade 3)	Potentially Life Threatening (Grade 4)
Illness or clinical AE (as defined according to applicable regulations)	No or minimal interference with usual activities; no medical intervention/therapy required	Greater than minimal interference with usual activities; no or minimal medical intervention/therapy required	Marked limitation in ability to perform usual activities; medical intervention/therapy required.	Inability to perform basic functions OR Medical or operative intervention indicated to prevent permanent impairment, persistent disability, or death
Acute systemic allergic reaction	Localized urticaria (wheals) with no medical intervention indicated	Localized urticaria with medical intervention indicated OR Mild angioedema with no medical intervention indicated	Generalized urticaria OR Angioedema with medical intervention indicated OR Symptomatic mild bronchospasm	Acute anaphylaxis OR Life-threatening bronchospasm OR laryngeal edema
Fever (non-axillary)	37.7 – 38.6°C	38.7 – 39.3°C	$39.4 - 40.5^{\circ}C$	> 40.5°C
Vomiting	Transient or intermittent vomiting with no or minimal interference with oral intake	Frequent episodes of vomiting with no or mild dehydration	Persistent vomiting resulting in greater than mild dehydration OR Aggressive rehydration indicated (e.g., IV fluids)	Life-threatening consequences (e.g., hypotensive shock)
Diarrhea	At least 3 looser-than-normal stools without dehydration	Diarrhea with some dehydration	Diarrhea with severe dehydration	Diarrhea with hypovolemic shock
Nausea	1-2 episodes within a 24-hour period	3-4 episodes within a 24-hour period	>5 episodes within a 24-hour period	
Abdominal Pain	Discomfort noted, but no disruption of normal daily activities; slightly bothersome; relieved with or without symptomatic treatment	Discomfort sufficient to reduce or affect normal daily activity to some degree; bothersome; interferes with activities, only partially relieved with symptomatic treatment.	Discomfort sufficient to reduce or affect normal daily activity considerably; prevents regular activities; not relieved with symptomatic treatment.	

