### **Exclusion criteria**

- 1. Presence of any significant known systemic disorder (cardiovascular, pulmonary, hepatic, renal, gastrointestinal, endocrine, immunological, dermatological, neurological, cancer or autoimmune disease) as determined by medical history and/or physical examination which would endanger the participant's health or is likely to result in non-conformance to the protocol.
- 2. History of congenital abdominal disorders, intussusception, abdominal surgery or any other congenital disorder or presence of a significant medical condition that in the opinion of the Investigator precludes participation in the study. Known or suspected impairment of immunological function based on medical history and physical examination. Clinical evidence of active gastrointestinal illness and acute disease at the time of enrollment
- 3. Screening positive with hepatitis B antigen and/or hepatitis C antibodies
- 4. Participation in research involving another investigational product (defined as receipt of investigational product) during the 30 days before planned date of first vaccination or concurrently participating in another clinical study at any time during the study period, in which the participant has been or will be exposed to an investigational or a non-investigational product
- 5. Clinically significant abnormalities in screening hematology or serum chemistry, as determined by the Study Physician
- 6. History of febrile illness within 48 hours prior to vaccination and fever at the time of immunization (fever is defined as a temperature ≥ 37.5°C (99.5°F) on axillary, oral, or tympanic measurement)
- 7. Prior receipt of any cholera (e.g., Dukarol, Shancol) or ETEC vaccine
- 8. Prior receipt of a blood transfusion or blood products, including immunoglobulins
- 9. Evidence of current illicit drug use or drug dependence
- 10. Current use of iron or zinc supplements within the past 7 days; current use of antacids (H2 blockers, omeprazole, OTC agents) or immunosuppressive drug
- 11. Any condition which, in the opinion of the investigator, might jeopardize the safety of study participants or interfere with the evaluation of the study objectives
- 12. Receipt of antimicrobial drugs for any reason within 14 days before vaccination
- 13. History of diarrhea during the 7 days before vaccination (see protocol definition of diarrhea)
- 14. Culture positive for ETEC, Shigella, V. Cholerae or Salmonella within 7 days before vaccination.

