### Post Dose – Observation Period

- a) Participants will remain at the site for at least 60 minutes post-vaccination for direct observation, and potential adverse events will be recorded in the CRF.
- b) The PI (or designee) may determine that a participant requires further on-site observation; additional site or clinical assessments may be completed as needed.
- c) The participant or parent/guardian will be reminded that eating or drinking, including breastfeeding is prohibited for one hour post-vaccination.
- d) Each participant will be provided with a symptom Memory Aid to record solicited symptoms on a daily basis through Day 7. Participants will be informed that a TSS will visit their home daily for 7 days to monitor their or their child's health, including taking temperature and recording any symptoms on a reactogenicity source document. The TSS will be responsible for that source document and bring it to and from the participant's home. TSS will review the information on the Memory Aid with the participant and interview the participant to elicit as much information as possible about any reported symptom(s). Based on information obtained from the participant, TSS should use their clinical judgment to assess the event and its severity and record the data on the reactogenicity source document. Participants will be instructed to bring the Memory Aid to the next scheduled clinic visit. Symptoms/signs solicited by the TSS and recorded on the source document will include the following: nausea (Part A only), abdominal pain/stomach ache (Parts A and B only), vomiting, diarrhea and fever.

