#### **Evaluation/Procedure Methods**

Study procedures are performed and recorded in source documents as outlined in the Schedule of Events (Appendix I) and according to the following subsections.

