#### Vital Signs

- Temperature in degrees Celsius (recorded to the nearest 0.1 degree) will be measured by axillary thermometer.
- Respiratory rate in breaths per minute will be measured by observation for a minute.
- Heart rate in beats per minute will be measured by automated device or manually.

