# Severe Diarrhea

Diarrhea with severe dehydration (per IMNCI definition)

*Dehydration:* Classification of the severity of dehydration will follow WHO guidance as well as criteria used at the icddr,b hospital (WHO 1990).

Grading the severity of adverse events in adults and children: toxicity grading scale for abnormal values will be based on Appendix II and Appendix III, respectively.

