# **APPENDIX III**

# PARTS B, C & D (TODDLERS, YOUNG CHILDREN & INFANTS) Clinical Toxicity Grading

Systemic Illness	Mild (Grade 1)	(Moderate (Grade 2)	Severe (Grade 3)	Potentially Life Threatening (Grade 4)
Illness or clinical AE (as defined according to applicable regulations)	No or minimal interference with usual activities; no medical intervention/therapy required	Greater than minimal interference with usual activities; no or minimal medical intervention/therapy required	Marked limitation in ability to perform usual activities; medical intervention/therapy required.	Inability to perform basic functions OR Medical or operative intervention indicated to prevent permanent impairment, persistent disability, or death
Acute systemic allergic reaction	Localized urticaria (wheals) with no medical intervention indicated	Localized urticaria with medical intervention indicated OR Mild angioedema with no medical intervention indicated	Generalized urticaria OR Angioedema with medical intervention indicated OR Symptomatic mild bronchospasm	Acute anaphylaxis OR Life-threatening bronchospasm OR laryngeal edema
Fever (axillary/orally)	≥ 37.5 - <38.5°C	≥ 38.5 - <39.5°C	≥ 39.5 – <40.5°C	≥ 40.5°C
Vomiting	Transient or intermittent vomiting with no or minimal interference with oral intake	>5 episodes within a 24-hour period	Persistent vomiting resulting in greater than mild dehydration OR Aggressive rehydration indicated (e.g., IV fluids)	Life-threatening consequences (e.g., hypotensive shock)
Diarrhea (≥3 loose stools/day)	At least 3 looser-than-normal stools without dehydration	Diarrhea with some dehydration (per IMNCI definition)	Diarrhea with severe dehydration (per IMNCI definition)	Diarrhea with hypovolemic shock
Abdominal Pain	Discomfort noted, but no disruption of normal daily activities; slightly bothersome; relieved with or without symptomatic treatment	Discomfort sufficient to reduce or affect normal daily activity to some degree; bothersome; interferes with activities, only partially relieved with symptomatic treatment.	Discomfort sufficient to reduce or affect normal daily activity considerably; prevents regular activities; not relieved with symptomatic treatment.	

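### Adult temperature is taken by axillary thermometer, but the only adult fever scale is labelled non-axillary and starts 0.2 °C above the protocol's own fever definition

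*Protocol*

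**What the plan says.** Five places in the protocol bear on adult fever.

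- **Measurement.** The Vital Signs section states: "Temperature in degrees Celsius (recorded to the nearest 0.1 degree) will be measured by axillary thermometer". It stands under Evaluation/Procedure Methods, which opens with "Study procedures are performed and recorded in source documents as outlined in the Schedule of Events (Appendix I) and according to the following subsections". No exception is made for adults.
- **Collection of the solicited event.** Staff visit the home daily for 7 days after each dose, "including taking temperature and recording any symptoms on a reactogenicity source document" (Post Dose – Observation Period). No other measurement site is named there.
- **Definition.** The Part A exclusion criteria say "fever is defined as a temperature ≥ 37.5°C (99.5°F) on axillary, oral, or tympanic measurement". The exclusion criteria for the second dose repeat this for all Parts.
- **Which scale applies.** The Clinical Definitions text, under Severe Diarrhea, says that for adults and children the "toxicity grading scale for abnormal values will be based on Appendix II and Appendix III, respectively".
- **The scales.** The adult row in Appendix II is headed "Fever (non-axillary)" and grade 1 runs from 37.7 to 38.6 °C. The paediatric row in Appendix III is headed "Fever (axillary/orally)" and grade 1 runs from 37.5 to below 38.5 °C.

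**The concern.** Taken together, these sections collect adult temperature at one site and grade it on a scale labelled for other sites. They also leave a band of adult readings that is fever in one part of the protocol and nothing in another.

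This touches a primary safety endpoint. The Sample Size Calculation and Safety Analysis sections count the proportion of participants with at least one solicited systemic reaction. The solicited events are nausea, abdominal pain, vomiting, diarrhea and fever. Fever is the only one that is not gastrointestinal, so it appears to carry this endpoint alone. That is an inference, because the protocol does not list the endpoint's members.

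The groups are small. With 15 adults per arm, one participant with an ungraded fever is 1/15 = 6.7 percentage points of that arm's rate. Fever grade also feeds the grade 3 criteria for pausing the study and for withdrawing a participant from further vaccination.

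**Working it through.** **Step 1: is there an adult scale for an axillary reading?** The measurement section gives axillary, the assignment rule gives Appendix II, and the only fever row there is non-axillary. The Toxicity Grading section refers to an Appendix X, which is not among the appendices at hand (I to IV). Its fallback to an external grading table covers laboratory values only. No scale for an adult axillary reading is found.

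**Step 2: where do the cut-offs differ?** The entry gap is 37.7 − 37.5 = 0.2 °C. Temperatures are recorded to 0.1 °C, so the two scales can be compared reading by reading. They differ only here:

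| Reading (°C) | Adult grade (Appendix II) | Paediatric grade (Appendix III) |
|---|---|---|
| 37.5, 37.6 | none | 1 |
| 38.5, 38.6 | 1 | 2 |
| 39.4 | 3 | 2 |
| 40.5 | 3 | 4 |

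The first row is also the band that the eligibility criteria call fever in adults. The difference does not run one way: at 39.4 °C the adult scale gives the higher grade.

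**Step 3: what could the site mismatch add?** The documents give no offset between sites. Suppose that an axillary reading is d below the site for which the scale was written. A temperature T at that site is then recorded as T − d and reaches grade 1 only if T ≥ 37.7 + d.

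- d = 0.2 °C (assumption): 37.7 + 0.2 = 37.9, so 37.7 and 37.8 °C go ungraded.
- d = 0.6 °C (assumption): 37.7 + 0.6 = 38.3, so 37.7 to 38.2 °C go ungraded.
- Grade 3 entry, 39.4 °C on the scale, would correspond to 39.4 + d, that is 39.6 to 40.0 °C.

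If d is zero, only the 0.2 °C gap of step 2 remains.

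**Step 4: does any stated figure change?** No. The plan's chance of at least one event in 15 participants is 1 − (1 − p)^15. This reproduces as 0.804 at p = 10.3% and 0.901 at p = 14.3%, against the stated 80% and 90%. That statement concerns serious events and events of special interest, not fever. As an illustration only, suppose that fever had a true rate of 14.3% and that 10%, 20% or 30% of fevers went ungraded (assumed shares). The chance of seeing at least one would fall from 90% to 87%, 84% or 79%.

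**The case against.** The strongest reply is that the site used at home visits is not settled. The axillary rule stands with heart rate and respiratory rate under Vital Signs, and the Schedule of Events lists vital signs apart from reactogenicity assessment and home visits. The eligibility criteria accept readings "on axillary, oral, or tympanic measurement". If adult home readings were oral, the Appendix II label would fit, and the earlier adult trial (OEV-121) used an oral limit of 37.7 °C. This weakens the certainty that a mismatch would occur in practice. It does not remove the contradiction, because axillary is the only site the protocol prescribes for taking temperature.

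It is also fair that 37.5 °C is an eligibility threshold and is never restated as the definition of the solicited event. A rule for dosing may differ from an entry grade.

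A reader might infer more than the text supports:

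- **That Part A fever is under-counted as a fact.** This holds only if events are counted by grade. Staff are told to use clinical judgment, and nothing says that an ungraded fever is left out.
- **That the comparison is tilted in favour of the vaccine or of dmLT.** All three Part A arms use the same scale. Whether dmLT goes forward rests on all available safety data, not on fever grade alone.
- **That the higher entry cut-off loosens the pause rule.** Adult grade 3 starts at 39.4 °C, below the paediatric 39.5 °C. Only the site mismatch could affect the rule, by an amount the documents do not give.

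Separate adult and paediatric scales may be deliberate, and no formal comparison of adults with children is planned. So the difference in scale matters for reading fever rates across the Parts, not for a test.

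**Conclusion.** The point holds as an inconsistency in how adult fever is measured, defined and graded. Two things are certain from the text. No grading scale is given for an adult axillary temperature, and adult readings of 37.5 and 37.6 °C are fever for dosing eligibility but have no grade as a solicited event.

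It follows that absolute Part A fever rates may be under-counted if events are counted by grade, and that they are not on the same scale as those of Parts B to D. The size beyond the 0.2 °C band cannot be computed, since the protocol gives neither a temperature distribution nor an offset between sites. The link to the primary endpoint rests on the inference that fever is its only member. Sample size and the planned comparisons between arms are unaffected.

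**What to change.** Reconcile the Part A exclusion criteria, the second-dose exclusion criteria, Vital Signs, Appendix II and Appendix III. Adult fever should then have one measurement site, one definition of solicited fever and a grading scale labelled for that site. State the site for home visits explicitly. The choice of site and cut-offs is the sponsor's.

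Record the site with each reading, and derive fever grades from the recorded temperatures on the agreed scale. The Toxicity Grading section has the investigator or designee assign grades, so the staff who grade need the corrected table too.

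The cost is an edit to the appendix and the sections named above, one field on the reactogenicity form, and re-derivation of any grades already assigned. No sample size or test changes.

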# **APPENDIX III**

# PARTS B, C & D (TODDLERS, YOUNG CHILDREN & INFANTS) Clinical Toxicity Grading

Systemic Illness	Mild (Grade 1)	(Moderate (Grade 2)	Severe (Grade 3)	Potentially Life Threatening (Grade 4)
Illness or clinical AE (as defined according to applicable regulations)	No or minimal interference with usual activities; no medical intervention/therapy required	Greater than minimal interference with usual activities; no or minimal medical intervention/therapy required	Marked limitation in ability to perform usual activities; medical intervention/therapy required.	Inability to perform basic functions OR Medical or operative intervention indicated to prevent permanent impairment, persistent disability, or death
Acute systemic allergic reaction	Localized urticaria (wheals) with no medical intervention indicated	Localized urticaria with medical intervention indicated OR Mild angioedema with no medical intervention indicated	Generalized urticaria OR Angioedema with medical intervention indicated OR Symptomatic mild bronchospasm	Acute anaphylaxis OR Life-threatening bronchospasm OR laryngeal edema
Fever (axillary/orally)	≥ 37.5 - <38.5°C	≥ 38.5 - <39.5°C	≥ 39.5 – <40.5°C	≥ 40.5°C
Vomiting	Transient or intermittent vomiting with no or minimal interference with oral intake	>5 episodes within a 24-hour period	Persistent vomiting resulting in greater than mild dehydration OR Aggressive rehydration indicated (e.g., IV fluids)	Life-threatening consequences (e.g., hypotensive shock)
Diarrhea (≥3 loose stools/day)	At least 3 looser-than-normal stools without dehydration	Diarrhea with some dehydration (per IMNCI definition)	Diarrhea with severe dehydration (per IMNCI definition)	Diarrhea with hypovolemic shock
Abdominal Pain	Discomfort noted, but no disruption of normal daily activities; slightly bothersome; relieved with or without symptomatic treatment	Discomfort sufficient to reduce or affect normal daily activity to some degree; bothersome; interferes with activities, only partially relieved with symptomatic treatment.	Discomfort sufficient to reduce or affect normal daily activity considerably; prevents regular activities; not relieved with symptomatic treatment.	

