### **Scientific Rationale**

As indicated above, the first generation inactivated whole cell vaccine when tested in child populations in Egypt and Bangladesh was reasonably immunogenic but presented tolerability issues, especially with regard to vomiting, amongst the lower infant age-groups when high vaccine doses were given (~10^11 bacterial cells). Encouragingly when fractional vaccine doses were given to infants in Bangladesh immune responses were noted with greatly improved tolerability. The 1stgeneration vaccine protected travelers against more severe forms of traveler's diarrhea [35]. However, in the one Phase 3 efficacy trial conducted in children, immunization of infants in Egypt did not result in significant protection. After the Phase 3 trials in travelers and infants were completed, a WHO review of the results resulted in recommendations which suggested that the vaccine could be improved by increasing the amount of CF antigen delivered with each dose as well as possibly giving the vaccine with a mucosal adjuvant [1]. The current formulation for the ETVAX vaccine addresses these recommendations and the recent completion of highly successful Phase I trials of safety and immunogenicity in Swedish adults supports the further evaluation of the safety and immunogenicity of this promising 2nd generation ETEC vaccine (ETVAX) among younger age-groups in an ETEC endemic area.

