#### **Safety Analysis**

The incidence of any adverse events (AEs) will be determined. Gastrointestinal and systemic AEs will be assessed postvaccination using participant/parent/guardian interview (including memory aids), targeted physical examinations, vital signs and clinical laboratory tests and reactogenicity assessments to be completed following each vaccination. The solicited AEs of nausea (Part A only), abdominal pain/stomach ache (Parts A and B only), fever, vomiting and diarrhea will be evaluated daily by the TSS for 7 days post vaccination. Unsolicited AEs will be assessed through Day 42 and serious adverse events (SAEs) will be assessed over the entire duration of the study. Proportions of subjects with events, overall, by grade and relationship with vaccination will be analyzed for each of the vaccine arms in comparison to the placebo arm. For the analysis of the solicited adverse events, the statistical comparisons using Fisher's exact test will be performed using two-sided 5% Type I error rate without an adjustment for multiple comparisons. The primary purpose of statistical comparisons are to screen potential AEs that need further clinical evaluation. Therefore they are not considered formal statistical hypothesis testing and it is acknowledged that there will be an inflated Type I error rate (i.e. inflated false statistical significances) due to performing multiple testing without an adjustment.

Safety will be assessed by analyses of the following primary endpoints (events), where the unit of analysis in each case will be the proportion of participants with at least one event:

- Solicited gastrointestinal reactions
- Solicited systemic reactions
- Unsolicited adverse events
- Adverse events where there is a reasonable possibility that the study product caused the event, i.e., are suspected adverse reactions
- Serious adverse events

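### The vomiting grades for Parts B to D (Appendix III) change criterion from grade to grade, so some events meet no grade and the grades do not rank severity

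*Protocol*

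**What the plan says.** The Protocol grades vomiting in the paediatric parts in Appendix III:

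- Grade 1: "Transient or intermittent vomiting with no or minimal interference with oral intake".
- Grade 2: a count only, five (or more than five) "episodes within a 24-hour period". The extracted text shows an underlined greater-than sign, most likely meaning 5 or more.
- Grade 3: "Persistent vomiting resulting in greater than mild dehydration OR Aggressive rehydration indicated (e.g., IV fluids").
- Grade 4: "Life-threatening consequences (e.g., hypotensive shock").

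The adult table in Appendix II uses a different Grade 2 for the same symptom: "Frequent episodes of vomiting with no or mild dehydration".

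The Toxicity Grading section says that an AE takes its worst grade over the course of the illness. It refers the grader to an external scale only for laboratory values that are not listed. Each appendix also has a general row for any illness or clinical AE, but nothing says that this row applies when a symptom has its own row and fits none of its grades.

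The grades are used in the Safety Analysis section: "Proportions of subjects with events, overall, by grade and relationship with vaccination will be analyzed for each of the vaccine arms". Under Safety Oversight, solicited reactogenicity is among the data that the IPST reviews before the next dose cohort opens. The Scientific Rationale explains why vomiting deserves care: the first-generation vaccine "presented tolerability issues, especially with regard to vomiting, amongst the lower infant age-groups when high vaccine doses were given".

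**The concern.** An ordinal severity scale needs two properties: every event falls in some grade, and a worse event never falls below a milder one. Here Grade 1 is set by feeding, Grade 2 by counting, and Grade 3 by hydration or treatment need. Nothing in Grade 2 picks up the child who fails Grade 1 because feeding is affected but has vomited only a few times.

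At stake is the grade distribution of the symptom that limited the earlier vaccine in the youngest children. Vomiting is solicited in all four parts and feeds a primary safety endpoint. If the table does not say where an event belongs, two assessors can grade the same child differently. Dose cohorts run one after another, so a change in grading habit over time would coincide with a change in dose level.

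**Working it through.** The plan gives no figure to reproduce. The check applies the row literally.

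**Conditions taken from Appendix III**

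- Grade 1 is met if vomiting is not persistent and its effect on intake is nil or minimal.
- Grade 2 is met if episodes in 24 hours ≥ 5 (alternative reading: > 5).
- Grade 3 is met if vomiting is persistent and dehydration is more than mild, or if aggressive rehydration is indicated.
- Grade 4 is left out, because no presentation considered is life-threatening.

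**Two children side by side**

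| | Child A | Child B |
|---|---|---|
| Vomits in 24 h | 3, not persistent | 6, not persistent |
| Effect on intake | more than minimal | none |
| Dehydration | mild | none |
| Aggressive rehydration | not indicated | not indicated |
| Grade 1 | fails on intake | met |
| Grade 2 | fails (3 < 5) | met on either reading |
| Grade 3 | fails | fails |
| Result | no grade | Grade 2 by the worst-grade rule |

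Child A gets the same result with 1, 2 or 4 vomits. If the cut is read as more than 5, it is the same with exactly 5.

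**Full grid**

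The grid crosses episodes (1 to 8), intake effect (2 levels), dehydration (none, mild, more than mild), persistence (yes, no) and aggressive rehydration indicated (yes, no): 8 × 2 × 3 × 2 × 2 = 192 presentations.

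- Cut read as 5 or more: 7 states of intake, dehydration and persistence have no grade at each count from 1 to 4, so 7 × 4 = 28 presentations. Another 80 meet more than one grade.
- Cut read as more than 5: 7 × 5 = 35 have no grade, and 66 meet more than one.

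The 28 split as follows. In 4 × 4 = 16, intake is affected more than minimally and dehydration is absent or mild, as in Child A. In 2 × 4 = 8, vomiting is persistent but intake is preserved and dehydration is at most mild. In 1 × 4 = 4, intake is affected and dehydration is more than mild, but vomiting is not persistent. The last two groups depend on reading transient and persistent as separate requirements; the 16 do not.

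These counts describe the logic of the table. They say nothing about how often each presentation occurs.

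**How many children**

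The only infant vomiting rate in the Protocol is in the section on studies in endemic areas: 4% at a quarter dose of the earlier vaccine, against 2.5% on placebo.

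- Infant dose group of 30: 0.04 × 30 = 1.2 infants vomiting.
- Toddler or younger-child dose group of 15, if the same rate held: 0.04 × 15 = 0.6.
- The share of these in the gap is not given. If it were a quarter to a half (an assumption), 0.3 to 0.6 of 30 infants would be affected.
- One regraded child moves a by-grade proportion by 1/30 = 3.3 points or 1/15 = 6.7 points.

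**The case against.** The strongest reply is that no event will in fact go ungraded. Trained staff are told to judge severity at each visit, the investigator or a designee assigns the grade, and the general illness row could be borrowed. That stands in part: the practical result is inconsistent grading rather than blank fields. But the protocol does not make the general row a fallback, so assessors may differ on whether to use it. The worst-grade rule helps only when at least one grade is met.

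Several stronger readings are tempting and are not supported:

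- **That the pause rules are compromised.** The solicited-event pause rule and the withdrawal criterion act at Grade 3. A child with at most mild dehydration and no need for aggressive rehydration is below Grade 3 on any reading.
- **That the primary endpoint is biased.** Its unit is the proportion of participants with at least one event. A vomiting child counts whatever the grade.
- **That the adult row already covers the case.** Its Grade 2 requires frequent episodes, which it does not define, and has no intake term. Three vomits may or may not qualify.
- **That adult nausea has the same hole.** Its Grade 3 reads ">5 episodes within a 24-hour period" after a Grade 2 of 3 to 4 episodes, so exactly 5 would have no grade. The Study Pause Rules print an underlined greater-than sign in two criteria where a parallel one prints ≥, so this is probably a lost symbol. It should be verified, not counted as an error.
- **That several infants per group would be affected.** This needs vomiting rates of, say, 10% to 20% (3 to 6 of 30), which the document does not give. Rates at higher doses are not stated.

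**Conclusion.** The point holds on the wording of Appendix III. The paediatric vomiting row is neither exhaustive nor ordered: one to four vomits with more than minimal interference with intake and no more than mild dehydration meets no grade, while a milder presentation with more vomits is Grade 2. Nothing else in the protocol closes the gap.

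Its reach is limited to the by-grade reactogenicity tables and the graded solicited data that the IPST sees between cohorts. The number of children is unknown and may be below one per dose group if the 4% rate applies to this vaccine, which is itself an assumption. The point is worth correcting because the symptom matters and the correction is cheap, not because a conclusion of the trial hangs on it. It rests on reading reduced intake as more than minimal interference, since otherwise Grade 1 applies, and on the row being applied as written.

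**What to change.** The sponsor and its clinicians should reconcile the vomiting row of Appendix III with that of Appendix II, so that Grades 1 to 3 are contiguous, cover every presentation and rise with severity. The clinical cut-offs are theirs to set. The Toxicity Grading section should state that an event meeting more than one grade at once takes the highest grade met, because the present sentence speaks only of the worst grade over the illness. The sponsor should also confirm whether the adult nausea Grade 3 is meant to include exactly 5 episodes, and whether the paediatric Grade 2 vomiting count does.

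The cost is about one table cell in Appendix III, one sentence, and the matching edit to the reactogenicity source form. The downside is that slightly more vomiting events may be reported as Grade 2.
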